5.2 Study Population

Target Population: Patients with heart failure (HF) eligible for CRT as part of routine standard-of-care based on accepted Class I or Class II indications will be considered for this study.

5.2.1 Approximate Number of Subjects

Approximately 100 Geisinger subjects will participate in this study; approximately 50 in the intervention arm, and approximately 50 in the control arm.

5.2.2 Inclusion Criteria

Eligible patients will be similar to those previously enrolled in the large randomized controlled trials and current Society guidelines^{18, 19} which support current indications for CRT. The following are the inclusion criteria for the HOT-CRT study:

1. Patients at least 18 years of age
2. Diagnosis is NYHA Class II, III, and ambulatory Class IV heart failure with either ischemic or nonischemic cardiomyopathy and patients with NYHA Class I symptoms and ischemic cardiomyopathy, with at least one of the following:
 - i. LV systolic dysfunction with LVEF \leq 35% and Evidence of bundle branch block with QRS duration $>$ 120 msec
 - ii. LV systolic dysfunction with LVEF \leq 50% and with need for $>$ 40% RV pacing

5.2.3 Exclusion Criteria

The following are exclusion criteria for the HOT-CRT study:

1. Existing CRT device
2. Inability of patient capacity to provide consent for themselves either due to medical or psychiatric comorbidity

- 3. Pregnancy
- 4. Participation in other device trials
- 5. Inability to complete study requirements

5.3 Recruitment

Subjects selected for the study will be recruited from Geisinger Wyoming Valley, Geisinger Medical Center, and Geisinger Community Medical Center for participation in the study. Investigators will identify eligible subjects during one of their initial, standard care visits, describe the study procedures and invite them to participate in the study. The Informed Consent Form (ICF) will be provided to the subject and they will have ample time and opportunity to review and consider participation. Prior to performing any study procedures, the subject will sign the ICF and be considered enrolled at that point. Documentation of the consent process will be entered into the subject's Electronic Health Record (EHR). The subject will be assigned a Study ID Number upon enrollment and their data will be entered into the study's database.

5.4 Study Duration

5.4.1 Approximate Duration of Subject Participation

Subjects will participate in the study for approximately 6 months. This includes the time from consent of the subject through a 6-month follow-up period.

5.4.2 Approximate Duration of Study

This study will be completed in approximately 24 months. This includes 3 months of study start-up, a subject recruitment period of approximately 12 months, 6 months of subject follow-up from the time of last subject enrolled and 3 months for data analysis.

5.5 Procedures & Study Timeline

Patients enrolled in the study will receive a permanent CIED (CRT-pacemaker or CRT-defibrillator) as clinically indicated. Patients will be centrally randomized by the study team with input from the biostatistician.

Procedure:

Patients randomized to biventricular pacing will undergo left ventricular lead placement in the coronary sinus venous branches.

Patients randomized to HOT-CRT will undergo CRT as described below. His bundle pacing lead will be placed initially to achieve CRT. If complete resynchronization is achieved (BBB normalization) but capture thresholds are high (1.5-2V), the lead may be placed in the distal conduction system (left bundle branch area). If only partial QRS narrowing is achieved, a coronary sinus lead may be placed and LV timing may be optimized to achieve maximal resynchronization. This will be at the discretion of the implanting physician.

Visit One - Pre-Implant

Enrolled subjects will undergo the following standard care procedures, unless noted as being completed for research purposes:

1. Clinical physical evaluation
2. Serum or urine pregnancy screen for women of child-bearing potential
3. Serum BNP or pro-BNP, baseline metabolic panel
4. Electrocardiogram
5. Transthoracic Echocardiogram (TEE) will be completed if it has not been done within the previous 3 months prior to Visit One.
6. Kansas City Cardiomyopathy Questionnaire (KCCQ) will be completed by the subject as part of the study
7. EuroQoL 5D (EQ-5D) will be completed by the subject as part of the study
8. Six Minute Walk Test (6MWT) will be administered by study staff to record distance as part of the study
9. NYHA functional class
10. Randomization – Subjects will be randomized by study staff in the study REDCap database to either HOT-CRT or standard BVP lead placement using a permuted block design. Patients will be blinded to randomization arm. Blocks of size 2 and 4 will be

randomly generated. Randomization will be stratified by LBBB and non-LBBB (right bundle branch block, RV pacing or narrow QRS) and by clinical site.

11. Collection of adverse events from time of consent until end of study participation

Visit Two – Day of Implant

1. Implant completed according to the assigned randomization arm by investigator
2. Electrocardiogram completed pre/post procedure
3. Device interrogation completed prior to hospital discharge
4. Adverse event collection

Visit Three – 2-week follow-up

1. Device Interrogation
2. Adverse event collection

Visit Four – 3-month follow-up

1. Clinical physical evaluation
2. Electrocardiogram
3. Device Interrogation
4. Adverse event collection

Visit Five – 6-month follow-up

1. Clinical physical evaluation
2. Electrocardiogram
3. Transthoracic Echocardiogram (TTE)
4. Device Interrogation
5. Kansas City Cardiomyopathy Questionnaire (KCCQ) will be completed by the subject
6. EuroQoL 5D (EQ-5D) will be completed by the subject
7. Six Minute Walk Test (6MWT) will be administered by study staff to record distance.

8. NYHA functional class
9. Adverse event collection

Remote device monitoring will be completed between visits as part of standard care of this patient population. Data from this monitoring will be collected as part of the study.

Any heart failure hospitalization (HFH), sustained ventricular arrhythmias requiring therapy (shock or ATP) or death will be documented. Heart failure hospitalization is defined as an unplanned outpatient or emergency department visit or inpatient hospitalization in which the patient presented with signs and symptoms consistent with heart failure and required intravenous therapy.

5.5.1 Participant Withdrawal

Subjects will be free to withdraw from the study at any time by notifying the study team in writing. If the subject withdraws, no further data will be collected after that timepoint unless needed for safety reporting.

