5 STUDY DESIGN

5.1 Description

This is a randomized, prospective, single-blinded trial. Patients will be randomized to HOT-CRT versus BVP and will remain blinded to their treatment allocation. Both treatment options use standard-of-care, FDA-approved devices. The distinction is only in the allocation toward HOT-CRT and BVP. Treating physicians will be aware of assignment in order to facilitate routine device follow-up. Echocardiographic evaluation will also be performed in a blinded manner. Study physicians with the role of completing this evaluation will be blinded to lead placement.

Crossover is permitted between treatment group allocation if:

- CS lead (BVP) cannot be placed due to difficult cannulation of the CS, limited branches at the posterolateral or lateral wall, or phrenic nerve capture. These patients may then crossover to HOT-CRT. All efforts will be made to achieve CRT using CS lead.
- HOT-CRT patients may crossover if HPCSP lead cannot be positioned with adequate stability and reasonable pacing output and acceptable electrical resynchronization cannot be achieved.

Implant procedure will be per routine percutaneous access, as is standard for pacemaker and implantable cardioverter defibrillators (ICDs). All patients will receive FDA-approved cardiac resynchronization therapy pacemaker or defibrillator device, as per standard of care outlined for the patient.

Follow-up will be performed at 2 weeks post-implant for incision check and device interrogation, as is standard of care. In addition, routine device and clinical follow-up will be scheduled at 3, and 6 months, with remote device monitoring between scheduled visits, as needed.

Electrocardiography (i.e., ECG) will be performed pre-implant, prior to hospital discharge, and at 3- and 6-months post-discharge, as is standard of care. Echocardiography will be performed pre-implant, at 6 months to evaluate for change in left ventricular ejection fraction (LVEF), chamber dimension, and wall motion with strain imaging as is standard of care in the treatment of patients with advanced heart failure. NYHA functional class and quality of life, as measured

by the Kansas City Cardiomyopathy Questionnaire (KCCQ) and the EuroQoL 5D (EQ-5D), will be assessed pre-implant and at 6 months.

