The primary clinical endpoint for the study (Aim 2) is change in left ventricular ejection fraction at 6 months. The primary safety endpoint (Aim 1) – freedom from major complications such as pericardial tamponade or need for CRT lead revision.

Secondary endpoints are as follows:

- Clinical: Composite of heart failure hospitalization, ventricular tachycardia (VT)/ventricular fibrillation (VF), crossover of treatment and any-cause mortality at 6 months will be assessed. NYHA functional class and quality of life will also be assessed.
- Electrocardiographic: Change in QRS duration between pre-implant and at hospital discharge, and 6 months will be performed. Arrhythmia occurrence (i.e., atrial fibrillation (AF), nonsustained VT, VT or VF requiring device therapy) will be documented throughout the study period.
- Echocardiographic: Change in left ventricular end-systolic volume index, chamber dimension, and tissue-strain pre-implant, and at 6 months will be performed by readers blinded to treatment allocation.

Regarding primary complication endpoints, complications will be assessed prospectively both acutely and throughout the study period, including:

- Procedure-related: pneumothorax, perforation, pericardial effusion, or hemorrhage
- System-related: implant site hematoma, implant site infection
- Lead-related: lead dislodgement, lead fracture, inability to pace due to high threshold, phrenic capture

Patients will be allocated to HOT-CRT or standard BVP (CS lead) prior to implant procedure. Randomization will be performed by the assigned biostatistician and use a randomly permuted block design. Blocks of size 2 and 4 will be randomly generated. Randomization will be stratified by LBBB and non-LBBB and clinical site.

Chart review will be performed for each enrolled patient upon study completion. The following events/data points will be collected to perform a survival analysis curve between the two randomized groups:

- Date of death and cause of death

- Heart failure hospitalization (HFH), date of HFH, and number of HFHs
- Atrial and ventricular arrhythmias as per device log
- Complications (i.e., lead revision, infection, device replacement, etc.)
- Last encounter date
- Last withdrawal date

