5.6 Primary Endpoints

The primary safety endpoint (Aim 1) – freedom from major complications such as pericardial tamponade or need for CRT lead revision. The primary clinical endpoint for the study (Aim 2) will be change in left ventricular ejection fraction at 6 months.

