5.8.2 Statistical Power and Sample Size Considerations

Analysis will follow the “intent-to-treat” principle. That is, subjects will be analyzed based on their randomization allocation. A small number of patients might cross-over into the other arm so we will complete a secondary analysis using the per-protocol principle where subjects are analyzed based on their final treatment allocation. Data will be fully described using mean and standard deviation or median and inter-quartile range for continuous measures, and frequency and percentage for categorical variables. Baseline variables will be summarized by randomization arm to assess for balance. Any imbalance will be adjusted for in the estimation of the parameters of interest. Successful placement (Aim 1) will be summarized in the HOT-CRT group among those randomized to this group. The percentage and 95% confidence interval will be estimated. A logistic regression model will be fit to identify baseline factors that associate with success. The primary endpoint in Aim 2, change in LVEF, will be estimated along with the

standard deviation and 95% confidence interval. The difference in change between the randomization arms will also be estimated. No formal statistical inferences will be conducted in this study. Deliverables

Pilot study deliverables will be to establish feasibility, collect preliminary data, and further develop and refine infrastructure to test hypothesis(es) in a fully powered trial. We anticipate being able to identify specific clinical and health care utilizations endpoints during the pilot trial, which will be important to further investigate in a larger, powered trial. We hope to publish our findings and add to the generalizable knowledge to inform physicians, policy-makers, and the healthcare community of real-world outcomes.

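### Withdrawal from the study (5.5.1) has a single consequence, so a routine-care 6-month LVEF goes uncollected although the intention-to-treat estimate needs it

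*Combined protocol and SAP*

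**What the plan says.** Section 5.5.1 defines withdrawal as a written act by the patient ("Subjects will be free to withdraw from the study at any time by notifying the study team in writing") and attaches one consequence: "If the subject withdraws, no further data will be collected after that timepoint unless needed for safety reporting". It has no intermediate level, such as ending study procedures while allowing routine records to be used.

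Four other places bear on this:

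- **Endpoint (5.6):** "The primary clinical endpoint for the study (Aim 2) will be change in left ventricular ejection fraction at 6 months".
- **Source of the endpoint (5.1):** the pre-implant and 6-month echocardiograms, including "wall motion with strain imaging as is standard of care in the treatment of patients with advanced heart failure". The visits are routine too: "routine device and clinical follow-up will be scheduled at 3, and 6 months, with remote device monitoring between scheduled visits, as needed". In 5.5, the items marked as done for the study are KCCQ, EQ-5D and the six-minute walk.
- **Chart data (5.1):** "Chart review will be performed for each enrolled patient upon study completion". The items feed a survival analysis and include death, heart failure hospitalization (HFH) and device-logged arrhythmias. Withdrawn patients are not excepted, though a withdrawal date is among the items.
- **Analysis (5.8.2):** intention-to-treat, so that "subjects will be analyzed based on their randomization allocation".

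Neither 5.8.1 nor 5.8.2 gives an expected withdrawal rate, an allowance for loss, or a method for a missing 6-month LVEF.

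**The concern.** A patient who leaves the study will often remain under the same health system's care and have the 6-month echocardiogram anyway. Under 5.5.1 the trial may not collect that LVEF, nor chart outcomes that fall outside safety reporting. The intention-to-treat estimate of the primary clinical endpoint then has a gap that could have been avoided at little cost, and nothing in the analysis plan fills it.

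Two things are at stake. The stated precision assumes that all 50 patients per arm contribute. And if leaving is related to outcome or to arm, the estimated mean change is biased. Section 5.8.1 says the pilot exists to supply parameters for a larger trial, so an error in the mean or SD would carry into that design. That there is no formal testing does not remove the concern, because the estimates are the product.

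**Working it through.** **Inputs from the documents.** SD of 6-month LVEF change 7.93; 50 patients per arm; stated 95% half-width 2.25 (all 5.8.1). **Assumed, because the documents give no figure:** the share of patients whose LVEF is lost to withdrawal, and how far their mean change differs from that of the others. The SD is held at 7.93 in both arms.

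**Step 1: reproduce the plan's figure.** Within one arm, half-width = t(0.975, n−1) × SD / √n.

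n = 50: 2.0096 × 7.93 / √50 = 2.254, which rounds to the stated 2.25. The normal quantile would give 2.198, so the plan used t with all 50 patients contributing.

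**Step 2: the difference between arms.** Half-width = t(0.975, 2n−2) × SD × √(2/n).

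n = 50: 1.9845 × 7.93 × √(2/50) = 3.147, or 3.15. The plan says it will estimate this difference but states no precision for it.

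**Step 3: repeat with assumed losses, equal in the two arms.**

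| Assumed loss | n per arm | Within arm | Difference |
|---|---|---|---|
| none | 50 | 2.25 | 3.15 |
| 4% | 48 | 2.30 | 3.21 |
| 10% | 45 | 2.38 | 3.32 |
| 20% | 40 | 2.54 | 3.53 |

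For the 10% row: 2.0154 × 7.93 / √45 = 2.382, and 1.9873 × 7.93 × √(2/45) = 3.322. The widening is 0.13 and 0.17 points, about 6% in each case.

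**Step 4: bias.** Let d be the share missing in an arm, and let the mean change be μr in retained and μw in withdrawn patients. The full-arm mean is (1−d)μr + dμw. An estimate from retained patients alone is therefore off by μr − [(1−d)μr + dμw] = d(μr − μw).

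Illustrations, with both inputs assumed:

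- 5% missing, 4-point gap: 0.05 × 4 = 0.2 points
- 10% missing, 4-point gap: 0.10 × 4 = 0.4 points
- 15% missing, 8-point gap: 0.15 × 8 = 1.2 points

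The error in the between-arm difference is the difference of the two arms' errors. It cancels if withdrawal works identically in both arms.

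**Step 5: compare the sections.** Section 5.1 orders chart review for every enrolled patient once the study is complete; 5.5.1 ends collection at withdrawal, apart from safety. Read together, the likeliest meaning is that review of a withdrawn patient's chart stops at the withdrawal date. The plan does not say so, and on that meaning the 6-month LVEF is still lost.

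**The case against.** Ending collection when someone leaves the whole study is a defensible, participant-protective choice, and intention-to-treat by randomized arm does not forbid it. The withdrawal date among the chart-review items suggests that follow-up was expected to stop there. This is an estimation-only pilot whose size was set by budget, and patients are blinded to arm, so frequent written withdrawal cannot be presumed. The consent form is not in the public document and may already separate the levels. A routine echo is also not a ready-made endpoint, since 5.1 calls for evaluation by study physicians blinded to lead placement. All of this stands. It limits the size of the point and shapes the fix, but it does not supply the missing LVEF.

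A reader might also infer more than the text supports:

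- *That all collection stops.* The rule excepts safety reporting. Under 6.1 to 6.3, deaths, inpatient admissions for an adverse event and major complications may still be captured, so part of the primary safety endpoint may survive. How far the exception reaches is unclear. It does not cover LVEF, and HFH as defined in 5.5 includes outpatient and emergency visits that need not meet the admission criterion.
- *That data are discarded.* The rule stops new collection; nothing says that data already held are dropped.
- *That a patient who declines only the questionnaires or the walk test is treated as withdrawn.* Section 5.5.1 concerns written withdrawal from the study and does not say this.
- *That crossover triggers the rule.* It does not; 5.8.2 keeps crossed-over patients in the analysis by randomized arm.

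**Conclusion.** The point holds in a limited form. For a patient who withdraws in writing, the plan forgoes a 6-month LVEF and non-safety chart outcomes that routine care may well produce. It offers no lesser level of withdrawal, gives no method for the missing value, and does not say how the chart review applies.

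The loss of precision is modest: at an assumed 10% loss per arm, the half-width goes from 2.25 to 2.38 within an arm and from 3.15 to 3.32 for the difference. Bias is the more serious possibility, but its size and direction are unknown. The 0.2 to 1.2 points shown are products of two assumed quantities, not a forecast.

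A reader might go further and say that dissatisfied or sicker patients will be the ones to leave, so that the result becomes a completers' estimate. The documents give neither a withdrawal rate nor any evidence on who withdraws, so they do not support that. This is a worthwhile low-cost improvement, not a flaw that undermines the pilot.

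**What to change.** In 5.5.1, and in the consent form if it does not already do so:

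1. Separate (a) stopping study-specific procedures (KCCQ, EQ-5D, six-minute walk, study contact) from (b) withdrawing permission to use medical records.
2. Under (a), where the patient permits it, keep collecting the routine 6-month echocardiogram, HFH, the arrhythmia log and vital status. Send the echocardiogram to the blinded study readers; do not take an unblinded clinical reading in its place.
3. Under (b), end collection, apart from the existing safety-reporting exception.
4. Record which level each patient chose, with the date.
5. In 5.1, state how the chart review applies to withdrawn patients at each level.

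The cost is protocol and consent wording with IRB review, plus the blinded reading of any echocardiogram retained. No visits or tests are added. The change does not help with LVEF missing through death or a missed echocardiogram.

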5.6 Primary Endpoints

The primary safety endpoint (Aim 1) – freedom from major complications such as pericardial tamponade or need for CRT lead revision. The primary clinical endpoint for the study (Aim 2) will be change in left ventricular ejection fraction at 6 months.

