2 ABSTRACT

Despite the great impact Cardiac Resynchronization therapy (CRT) utilizing biventricular pacing (BVP) has had on heart failure patients, one-third of patients do not respond to CRT, and CRT may result in worsening heart failure and increased mortality in some patients. We hypothesize that in patients with heart failure (HF) eligible for CRT as part of routine standard-of-care based on accepted Class I or Class II indications, His-Purkinje conduction system pacing (HPCSP)-optimized trial of CRT (HOT-CRT) may not only be safely achieved but will also be associated with superior echocardiographic and clinical outcomes compared to conventional BVP during CRT. We aim to determine the overall rate of successful HOT-CRT at the time of implant of CRT in a pilot study, collecting data in BVP and HOT-CRT on acute and mid-term outcomes at Geisinger. Primary outcomes include freedom from major complications and change in left ventricular ejection fraction (LVEF) at 6 months. To compare the effectiveness of HOT-CRT versus traditional CRT in patients with heart failure, patients will be randomized to either HOT-CRT or BVP and will remain blinded to their treatment allocation. Treating physicians will be aware of assignment in order to facilitate routine device follow-up. Echocardiographic evaluation will also be performed in a blinded manner. Crossover is permitted between treatment group allocation as follows: (1) If CS lead (BVP) cannot be placed due to difficult cannulation of the CS, limited branches at the posterolateral or lateral wall, or phrenic nerve capture, patients may then crossover to HOT-CRT. All efforts will be made to achieve CRT using CS lead. (2) HOT-CRT patients may crossover if HPCSP lead cannot be positioned with adequate stability and reasonable pacing output and acceptable electrical resynchronization cannot be achieved. Echocardiographic response to CRT (improvement in left ventricular ejection fraction) and a combination of clinical, electrocardiographic, and echocardiographic endpoints will be prospectively studied. Any complications will also be assessed prospectively, both acutely and throughout the study period.

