3.1 Hypothesis

We hypothesize that:

1. in patients with advanced heart failure and evidence of intraventricular conduction disease who meet criteria for CRT, HOT-CRT may be safely achieved and,
2. HOT-CRT will be associated with superior echocardiographic and clinical outcomes compared to conventional biventricular pacing (BVP) during CRT.

3.2 Specific Aim 1

To determine the overall rate of successful HOT-CRT at the time of implant of CRT. Patients randomized to HOT-CRT but who cannot be successfully implanted with a HPCSP lead will crossover to traditional coronary sinus (CS) lead position.

3.3 Specific Aim 2

To perform a pilot study to collect data in BVP and HOT-CRT on acute and mid-term outcomes at Geisinger. Acute outcomes include change in QRS duration pre-and post-pacing (degree of QRS narrowing) and incidence of major periprocedural complications (pericardial tamponade, need for lead revision, etc.). Mid-term outcomes include echocardiographic response at 6 months along with a composite clinical outcome of heart failure hospitalization, ventricular arrhythmias, crossover, and all-cause mortality.

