4 PRELIMINARY DATA

In patients with bundle branch blocks (BBB), capture thresholds to correct the BBB may limit the ability to achieve successful HBP. High pacing thresholds may lead to premature battery depletion. Recently an alternative form of conduction system pacing has gained significant momentum. By pacing distal to the site of conduction block in the proximal left bundle via deep lead placement in the interventricular septum, very low and stable capture thresholds can be achieved.^{13,14,15,16,17} This new approach, called left bundle branch pacing (LBBP), has been shown to achieve significant narrowing of the paced QRS and improve clinical outcomes in patients with LV dysfunction and LBBB. In short- and medium-term follow-up, this approach has been shown to be feasible in a very high percentage of patients.

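### Does the loosely defined primary safety endpoint, with its conflicting aim label and no named confidence interval, need a change to the plan?

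*Combined protocol and SAP*

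**What the plan says.** The abstract (Section 2) states: "Primary outcomes include freedom from major complications and change in left ventricular ejection fraction (LVEF) at 6 months". Sections 5.1 and 5.6 define the safety endpoint as "freedom from major complications such as pericardial tamponade or need for CRT lead revision" and tie it to Aim 1.

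The aims read differently. Section 3.2 gives Aim 1 as "To determine the overall rate of successful HOT-CRT at the time of implant of CRT". Section 3.3 places complications under Aim 2, among the acute outcomes, as "incidence of major periprocedural complications (pericardial tamponade, need for lead revision, etc", so the list is left open there too.

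Section 5.1 also introduces a list with "Regarding primary complication endpoints, complications will be assessed prospectively both acutely and throughout the study period, including". The list covers procedure-related, system-related and lead-related events. None is marked major or minor.

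Section 5.8.2 ties Aim 1 to successful placement in the HOT-CRT arm, with a percentage and a 95% interval. It plans an estimate, standard deviation and 95% interval for LVEF change. Categorical variables in general get counts and percentages. The section does not mention the safety endpoint by name and rules out formal inference. Section 5.8.1 adds a between-arm time-to-event analysis, and Section 5.1 lists complications among the data collected for the survival curve.

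**The concern.** A primary endpoint should be fixed before results are seen. This one is given only by examples, under a label that leads elsewhere: a reader who follows Aim 1 into Section 5.8.2 finds placement success in one arm and no safety analysis. The first hypothesis in Section 3.1, that HOT-CRT can be achieved safely, depends on this endpoint.

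Three things seem to be at stake.

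- **What counts.** The Section 5.1 list runs from perforation to hematoma and phrenic capture with no severity threshold, so the choice of what is major could be made late.
- **Crossover.** In the BVP arm a reason to cross over is "or phrenic nerve capture. These patients may then crossover to HOT-CRT", and phrenic capture is also a listed complication. In the other arm, "HOT-CRT patients may crossover if HPCSP lead cannot be positioned with adequate stability and reasonable pacing output", while inability to pace because of a high threshold is listed as well. The plan does not say whether such implant-time events count as safety failures.
- **Precision.** A pilot meant to supply parameters for a larger trial should show how uncertain its complication rate is, and no interval is named.

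**Working it through.** **The plan's own figure.** Section 5.8.1 gives a half-width of 2.25 for LVEF change, with SD 7.93 and 50 per arm. The formula is t(0.975, 49 df) × SD / √n, which gives 2.254 and reproduces it. (With 1.96 in place of t the result is 2.198.) No figure is stated for safety.

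**What the missing interval would show.** The documents give no complication rate, so the event counts below are assumptions, with all 50 patients per arm in the denominator. The exact (Clopper-Pearson) limits for x events are the 2.5% quantile of Beta(x, n − x + 1) and the 97.5% quantile of Beta(x + 1, n − x). For x = 0 the upper limit is 1 − 0.025^(1/50) = 7.1%.

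| Events of 50 | Rate | Exact 95% CI | Free of complications, 95% CI |
|---|---|---|---|
| 0 | 0% | 0 to 7.1% | 92.9 to 100% |
| 2 | 4% | 0.5 to 13.7% | 86.3 to 99.5% |
| 5 | 10% | 3.3 to 21.8% | 78.2 to 96.7% |
| 8 | 16% | 7.2 to 29.1% | 70.9 to 92.8% |

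The only inputs are x and n. Section 5.8.2 already promises the count and the percentage, so any reader can obtain these limits. Naming them in advance adds convenience but no information.

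For a between-arm difference, Newcombe's interval with equal arms is ±9.9 points at 2 against 2 events and ±12.7 points at 5 against 5. The plan says that the LVEF difference will be estimated and names no interval for that difference either, so safety is not treated worse there.

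**What the open definition could move.** One event is 1/50 = 2 points. If a narrow reading gave 2 events and a broad one 8 (both assumed), the rate would go from 4% to 16%, a shift of 12 points.

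**The window.** Section 5.6 gives none and Section 3.3 says periprocedural. However, the Section 5.1 text quoted above covers the acute phase and the whole study, Section 5.4.1 sets participation at about 6 months, and Section 6.2 records adverse events from consent to the end of follow-up. The periprocedural count is then the acute part of the same series.

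**Crossover events.** These are not lost. Crossover is a component of the secondary composite in both arms (Section 5.7), and failed placement in the HOT-CRT arm enters the placement-success rate (Section 5.8.2).

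**Direction of any shift.** Section 4 says that "capture thresholds to correct the BBB may limit the ability to achieve successful HBP". That concerns correcting the block, not inability to pace. The same section reports low, stable thresholds with left bundle branch pacing, and Section 5.5 lets HOT-CRT patients receive a lead in the left bundle area or a coronary sinus lead. The documents therefore do not tie the listed high-threshold event to one arm.

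**The case for a change.** The strongest reply concerns the definition. Section 5.5 defines heart failure hospitalization carefully, although it is only one component of a secondary composite, while the primary safety endpoint has no comparable definition. Treating physicians know the assignment (Section 5.1), the principal investigator assesses events and causality (Section 6.1), and no independent adjudication is described. The absence of formal inference is no full answer either, since the same section plans intervals for other outcomes.

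Much of this stands as description. A closed list would be tidier, and an interval would be normal good reporting. But the remedy would only ask the sponsor to write down a list and threshold that the documents do not supply, so it corrects no error in them. Nor is a crude proportion with an exact interval clearly better than what is planned. Section 5.5.1 generally stops data collection at withdrawal, and randomization at Visit One precedes implant. A simple proportion would need denominator rules for withdrawals, deaths and patients never implanted. The survival analysis already planned handles withdrawal by censoring.

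**Conclusion.** The observations are correct, but they amount to a labelling slip plus detail that analysts can fill sensibly. The aim label changes no calculation. The window can be read from Sections 5.1 and 5.4.1. The missing interval costs the reader nothing once the count is reported: at 50 per arm it would run from 0 to 7.1% with no events and from 3.3 to 21.8% with five.

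What remains is the meaning of major, worth 2 points per event in an arm. That uncertainty is real and its direction is not known in advance. It is contained because the event types are named and collected prospectively; if counts are shown by type and arm, a reader can see what drives the total and apply a narrower or broader definition. The study estimates parameters for a later trial and makes no formal inference, so error control and sample size are untouched.

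This rests on two assumptions: that complications are reported by type under the general summary rule, and that the 50 per arm are largely followed to 6 months. On that footing no change to the plan is needed.
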